### **Expected Outcomes**

Based on our pilot study, it is reasonable to expect that mothers in Group 1 (earliest expression of milk) will have the earliest onset of lactogenesis stage II, produce the most milk overall and have infants who are provided increased breast milk during hospitalization and at discharge.

## **Data Entry and Management**

All data will be entered into a REDCap database having integrated data quality and consistency checks (e.g., data-range) as part of the data procedure. REDCap is a secure, web-based application for building and managing online surveys and databases. Using REDCap's stream-lined process for rapidly developing projects, projects are designed and created online from a web browser using the Online Designer or by constructing a 'data dictionary' template file in Microsoft Excel, which is uploaded into REDCap. Both surveys and databases can be built using these methods. REDCap provides automated export procedures for seamless data downloads to Excel and common statistical packages (SPSS, SAS, Stata, R), as well as a built-in project calendar, a scheduling module, ad hoc reporting tools, and advanced features, such as branching logic, file uploading, and calculated fields. The study database created in REDCap will be password-protected and housed on a designated database server, which is protected by a computer firewall. Data quality will be monitored and assured: 1) as reported; and 2) as entered into the database. For the former, all hardcopy forms will be visually inspected before data entry. Furthermore, a manual comparison of randomly selected data hardcopy forms with data output listing generated from the study database will be performed, and consistency checks will be generated by SQL or SAS programs as part of routine data cleaning procedures.

All subjects eligible for enrollment will be registered and entered into the study database designed by the program assistant. The system includes designated web servers and supporting database servers. Study data will be directly entered into the database via a secure internet connection. The system allows the PI to access data in real-time and to generate reports based on enrollment status, basic demographics, and data summaries. The web-based data system will also allow for the sharing of data in the future. The system will assign a global unique identifier to each enrolled subject that will serve as the unique subject id. Personal Health Information will not be stored in the study database. The study case report forms (CRFs) will be maintained in study specific folders. The CRFs are considered the primary data collection instruments for this study. When CRFs are not actively being processed, they will be secured in locked file cabinets. In addition to the use of passwords and other security measures, all documents containing identifying information are considered confidential materials and are safeguarded to the greatest possible extent. No individually identifying information will be released or discussed with anyone other than study staff.

## **Potential Problems and Alternative Strategies**

The most likely potential problem is difficulty retaining subjects in the study between consenting prior to delivery and initial breast milk expression. Although our pilot study indicated this dropout to be highly unlikely, to minimize this problem a member of the research team will be available to the mother to help her pump the first time (at the time designated). Should she chose to pump at a different time (earlier or later), then she will receive the standard care available to her from the nursing staff and will no longer be eligible for the study.

Another problem related to retention is the continued willingness of mothers to express milk at the frequency required and for the duration of the study (at least 5 times a day until attainment of lactogenesis stage II). While this frequency may appear burdensome, these are the standard directions provided to mothers of VLBW infants receiving standard care i.e. who are not enrolled in the study.

A third potential problem is retention of the mother in the study for 6 full weeks post-delivery, when many women stop pumping due to lack of breast milk. To encourage mothers to continue trying to express their milk, each mother will be assigned to a graduate research assistant with experience involving the care of lactating women. This same student RA will contact the mother three times per week, either in person in the hospital or via telephone. The student will remind the mother to continue to pump at least 5 times per day and to bring in her breast milk with every visit. The role of student RAs in maintaining contact with mothers will decrease the likelihood of contamination of data collection procedures, since the PI or one of the co-investigators could inadvertently provide lactation consultation during the calls.

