### Randomization

Table 1. Randomization and Stratification of Mothers

Gestational Age	Group 1 Early Expressers	Group 2 Intermediate Expressers	Group 3 Late Expressers
23-27 weeks	0-60 minutes	61-180 minutes	181-360 minutes
28-32 weeks	0-60 minutes	61-180 minutes	181-360 minutes

mothers into groups. Following the birth of an infant weighing less than 1500 grams, with a gestational age between 23-32 weeks, mothers who continue to meet inclusion criteria will be stratified according to the gestational age of the infant (23-27 weeks and 28-32 weeks). Gestational age will be determined through one of the following; 1st or 2nd trimester ultrasound or the average of the obstetric gestational age and the results of the Ballard exam. This stratification is based upon likely differences in breast milk production in mothers who deliver earlier in gestation due to decreased mammary gland development and decreased levels of prenatal hormones necessary for preparation of the breast for lactation.

Following stratification, mothers will be randomly assigned to one of three groups to begin milk expression at different time periods following delivery. Group 1 (early expressers) will begin milk expression 0-60 minutes following delivery, Group II (intermediate expressers) will begin 61-180 minutes following delivery, and Group III (late expressers) will begin 181-360 minutes following delivery. The selection of the time periods for the groups is based upon our preliminary data showing greater milk volume and earlier lactogenesis stage II in women who began milk expression within 1 hour following delivery compared to those who began milk expression 1-6 hours following delivery (Parker et al., in press).

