### Primary Aim

The primary aim of this study is to compare over; the infant's hospitalization the effect of timing of initiation of breast milk expression on timing of lactogenesis stage II and amounts of breast milk produced during the following time periods:

- (a) early (within 1 hour of delivery),
- (b) intermediate (within 2-3 hours) and
- (c) late (within 3-6 hours).

Once mothers are randomly assigned to one of the three intervention groups, the research coordinator, the PI, or a research assistant experienced with lactation will meet with the mother at the designated time, confirm her continued consent, and assist her with her first breast pumping session using a hospital grade breast electric breast pump. Mothers who have recently delivered premature infants often take time to recover from anesthesia and may be clinically unstable. Since these mothers cannot always express their breasts independently, the above research team members will assist these mothers with milk expression. All research team members who assist mothers with the initial milk expression session will either be certified lactation consultants or have extensive training in lactation and milk expression. Assistance may range from education to actually performing the milk expressing for the mother. In the pilot study, all mothers randomized to milk expression within one hour were able to have their breasts expressed within the first hour following delivery. Since individuals assisting mothers with the initial breast expression may be required to have significant involvement in the milk expression process, they will be evaluated prior to assisting mothers and their skills will be monitored bimonthly by the research coordinator or PI to ensure that a safe and standardized procedure is used. Furthermore, a procedure checklist will be used to ensure consistent information and instruction is provided to all mothers (Appendix A). Following the initial milk expression session, mothers will receive the standard written and verbal pumping instructions provided to all of the mothers who are pumping breast milk for their infants (Appendix B). Information regarding maternal factors will be collected by a research team member (Appendix C)

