#### Design/Analysis Issues.

Analysis sets. For primary analyses the intent-to-treat (ITT) sample will be used comprising all randomized mothers patients. Secondary per-protocol (completer) analysis will include mothers who were compliant with protocol requirements and for whom all required measurements have been made. ITT and per-protocol analyses will be compared to test the sensitivity of our conclusions to non-adherence/attrition.

Missing data. Every attempt will be made by the study coordinator to keep mothers in the study, with the help of the student research team members and to obtain required measurements in order to ensure the completeness of the study data. To minimize potential bias due to missing observations, mothers will be contacted by phone if vials of expressed breast milk are missed, and reasons for missing data will be carefully documented. Subject participation will only be terminated due to safety reasons for mother and infant, withdrawal of consent, or loss to follow-up. Several approaches to handle missing data in the ITT analysis set will be employed. For continuous variables using a single end-of-study value (e.g., amount of milk expressed at day 42), Little and Rubin's multiple imputation methods will be used (Little & Rubin, 1997). For analyses of longitudinal outcome data, we will use longitudinal methods (e.g. mixed models) capable of dealing with missing data (Hedeker & Gibbons, 2006).

Multiple outcome variables. In order to address possible Type I errors due to the number of outcome variables, we specify the primary outcome measures a priori corresponding to the stated a priori hypothesis and maintain the alpha (significance) level at 0.02. For analysis of secondary outcome variables, we will further adjust resulting p-values using Bonferroni-type corrections for multiple outcomes. Both unadjusted and adjusted p-values will be reported.

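### Removing randomised mothers who pump outside their assigned time conflicts with the all-randomised primary analysis and the closed list of reasons for ending participation

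*Combined protocol and SAP*

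**What the plan says.** Three parts of the combined protocol and SAP bear on this.

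- **When the time is assigned.** Randomization places allocation after birth: "Following stratification, mothers will be randomly assigned to one of three groups to begin milk expression at different time periods following delivery". The windows are 0-60, 61-180 and 181-360 minutes. Primary Aim then has a member of the research team, who "will meet with the mother at the designated time, confirm her continued consent, and assist her with her first breast pumping session".
- **What happens if she picks another time.** Potential Problems and Alternative Strategies covers a choice in either direction. She gets the standard care available "from the nursing staff and will no longer be eligible for the study". The same paragraph plays down how often this will occur: "Although our pilot study indicated this dropout to be highly unlikely".
- **Who is analysed and who may leave.** Design/Analysis Issues, Analysis sets: "For primary analyses the intent-to-treat (ITT) sample will be used comprising all randomized mothers patients". Non-compliance is handled in a secondary per-protocol set, and "ITT and per-protocol analyses will be compared to test the sensitivity of our conclusions to non-adherence/attrition". The Missing data paragraph of that section restricts the ending of participation to three grounds: safety of mother or infant, withdrawal of consent, and loss to follow-up.

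**The concern.** Start time is the intervention. Removing a mother because she did not start at her assigned time is an exclusion after randomisation, made on the randomised variable. The primary set would then be a modified ITT set without the timing non-adherers. It would still differ from the per-protocol set, which also requires other compliance and complete measurements.

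Two things are at stake. First, the planned comparison of ITT with per-protocol cannot test sensitivity to timing non-adherence if those mothers are in neither set. Second, the three windows make different demands on a mother who has just delivered, so removals may differ by arm and may be related to milk output. If follow-up stops on removal (an inference; the plan does not say), multiple imputation and the mixed model have no later data from these mothers, and data never collected cannot be recovered at analysis.

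**Working it through.** **1. The rules side by side.**

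| Question | Potential Problems and Alternative Strategies | Design/Analysis Issues |
|---|---|---|
| May participation end because she chose another pumping time? | Yes | No; not among the three permitted grounds |
| Is she in the primary set? | Not stated; removal implies no outcome data | Yes; she was randomised |
| Where is timing non-adherence handled? | By removal from the study | By leaving her out of the secondary per-protocol set |

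The order of events settles whether she has been randomised. Randomization assigns the time after birth and stratification, Procedure puts randomisation before the first assisted session, and the removal rule is triggered by departure from the designated time. A mother to whom the rule applies has therefore been randomised.

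**2. The plan's own figure.** Sample Size Determination / Power Analysis gives 85% power for 34.1 hours in time to lactogenesis II (SD 55.0, 60 per group, two-sided alpha 0.02). With power = Φ[δ/(σ√(2/n)) − z(0.99)], 34.1/55.0 = 0.62, 0.62/√(2/60) = 3.396, and Φ(3.396 − 2.326) = 85.8%. The noncentral t version gives 84.9%. The stated 85% reproduces.

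**3. Loss of numbers (removal shares assumed).** By the same normal formula, removing 5, 10, 15 or 20% from every arm leaves 57, 54, 51 or 48 per group and 83.7, 81.5, 78.9 or 76.1% power. This is a modest loss.

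**4. Selection (shares and gaps assumed).** Let p be the share of one arm removed and g the retained mean minus the removed mean, in SD units. The arm mean shifts by p × g. The plan gives a milk-volume SD of 250 and a planning effect of 125 mL. Type I error uses the noncentral t at two-sided alpha 0.02, with 60 against 60(1 − p), removal in one arm only and SD unchanged. The last column is for the mean of 13 time points with intra-class correlation 0.5: variance factor (1 + 12 × 0.5)/13 = 0.538, normal approximation.

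| p | g (SD) | Shift (SD) | Shift (mL) | Share of 125 mL | Type I error, one time point | Type I error, mean of 13 |
|---|---|---|---|---|---|---|
| 5% | 0.25 | 0.0125 | 3.1 | 2.5% | 0.0203 | 0.0205 |
| 10% | 0.5 | 0.05 | 12.5 | 10% | 0.0244 | 0.0284 |
| 20% | 1.0 | 0.20 | 50 | 40% | 0.0961 | 0.179 |

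At 5% removal, the total dropout anticipated in Sample and Setting, gaps of 0.25 to 1.0 SD give 0.05 × 0.25 × 250 = 3.1 mL to 0.05 × 1.0 × 250 = 12.5 mL.

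**5. Direction.** Remove 10% from both the early and late arms with a 0.5 SD gap in each. If the gaps have the same sign, the early-late contrast moves by 0.10 × 0.5 − 0.10 × 0.5 = 0. If they are opposite, it moves by 0.05 + 0.05 = 0.10 SD = 25 mL. The sign is therefore open.

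**The case against.** The strongest reply is that the removal rule says nothing about analysis sets. A removed mother could stay in the ITT set with missing outcomes, to be handled by imputation and mixed models. This is fair as to wording: exclusion from ITT is inferred, whereas the clash with the three permitted grounds is direct. It does not resolve the conflict, because the plan nowhere provides for collecting her later outcomes, and a mixed model has little to work with when every outcome is missing.

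Second, declining the assigned session might be treated as withdrawing consent, since consent is reconfirmed at that point. The documents do not say so, and a mother can pump at another time and still be willing to have her milk weighed.

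Third, the paragraph is framed around retention from consent to first expression, part of which precedes randomisation. The trigger, departure from a designated time, nevertheless presupposes assignment.

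Fourth, the event may be rare. The paragraph says so, and Primary Aim reports that "In the pilot study, all mothers randomized to milk expression within one hour were able to have their breasts expressed within the first hour". That evidence covers the early arm only, but the point stands: no material bias has been shown. The 20% and 1.0 SD case has no support in the documents and should carry no weight in judging severity.

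**Conclusion.** The concern holds. The two sections give incompatible instructions for the same randomised mother, and following the removal rule as written is a post-randomisation exclusion on the randomised variable. The need for correction rests on that contradiction about the primary analysis set, not on a demonstrated bias. The size is not established: at the anticipated 5% it would be about 3 to 12.5 mL in one arm, or 2.5 to 10% of the planning effect, under assumed gaps of 0.25 to 1.0 SD, and the direction is unknown. The conclusion assumes that loss of eligibility ends follow-up or takes her out of the analysed set, which is the natural reading but is not spelled out.

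**What to change.** In Potential Problems and Alternative Strategies, keep the part on standard care and replace the loss of eligibility with:

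> Unless she withdraws consent, the mother stays in follow-up under the existing milk-weighing and lactogenesis II procedures, her actual start time is recorded, and she is analysed in her assigned group. An off-window start is a protocol deviation that excludes her only from the secondary per-protocol set.

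Report the number of off-window starts by arm, with reasons. This applies the scheme already set out in Design/Analysis Issues. As worded, it also covers starts delayed for clinical or staffing reasons, which the present rule does not address; the sponsor should confirm that this is intended.

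The cost is one protocol sentence and, if 5% start off-window (assumed), follow-up of about 0.05 × 60 = 3 more mothers per arm using the existing weighing, daily questions and reminder contacts, plus the home pump each enrolled mother receives. The sponsor should check that the consent terms cover this follow-up; those pages were not available to this review. There are two statistical downsides: slight dilution of the contrast between arms, and initial-expression volumes that may be missing or recorded by nursing staff for these mothers, because the research team assists only at the designated time.

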## **Potential Risks**

Milk expression procedures for mothers in this study will be the same as if they were not in the study; therefore, there is no more risk for participants than there would be in day-to-day life. If lactation problems occur, including nipple pain, problems with the mechanical pump, or breast discomfort, this information will be communicated to a lactation consultant in the Neonatal Intensive Care Unit. Infants' involvement will be purely observational, and therefore there is no risk added by their inclusion in the study.

In this study, the mothers will likely be expressing their milk earlier than standard clinical practice dictates. In our pilot work, mothers who initiated milk expression within one hour of delivery had less pain and stress associated with the initial milk expression session than those who began milk expression 1-6 hours following delivery. Therefore, those in the Intermediate and Late Expressers groups are more likely to experience discomfort. However, this discomfort is expected to be fleeting and no different than the discomfort the mother would have experienced in usual clinical care. It is important to note that initial milk expression will be facilitated only by the research coordinator, the PI, or a research assistant experienced with lactation. Ongoing lactation support will be the same for all lactating mothers in the NICU and will include lactation services and support by the nursing staff.

The PI will notify maternal subjects of new information that may become available and which might affect their decision to remain in the study. Because the subjects will be low-risk, the categorization of level of risk is minimal or the probability of harm or discomfort is not anticipated or greater than those encountered during the routine care. **Alternative treatments** include discontinuation of milk expression.

All documents will be de-identified using a subject number and filed within a locked filing cabinet within the PI's research space.

### **Potential Benefits of the Proposed Research to Human Subjects and Others**

Benefits are relevant to the NIH mission to enhance health and reduce the burdens of illness for preterm infants. This study is expected to make a significant contribution to understanding the effects of alternative timing of initiating milk expression following delivery in mothers of VLBW premature infants. This research will provide the knowledge to decrease time to lactogenesis stage II and increase milk production thereby increasing the amount of breast milk fed to VLBW infants and decreasing the complications and costs associated with premature births. These results can be translated into practice by influencing protocols regarding initiation of milk expression for mothers of VLBW infants in labor and delivery, post partum units, and NICUs.

Mothers of VLBW infants will benefit from this study by having a greater production of breast milk and an earlier lactogenesis stage II because they will begin milk expression earlier than standard care requires. Mothers will also benefit from this study because they will be given a hospital grade pump for home-use for the duration of the study.

### **Conflict of Interest**

There are no conflicts of interest to report
